#### Month 15 Visit

At month 15, a tele (audio/visual) visit will be performed, the following assessments will occur:

- Administer Neuro/Motor Assessments per the SOA (Table 1)
- Administer Cognitive and Psychiatric Assessments: Cognitive Change and Cognitive Characterization
- Administer C-SSRS Since Last Visit Short Form
- Digital Assessment per the PPMI Digital Sub Study (as needed)
- Concomitant medication review
- LEDD medication initiation log (as needed)
- Assess and document AEs
- Current medical conditions review
- Report of Pregnancy (as needed)
- Surgery for PD (as needed)

Please note, this visit can be converted to an in-person visit if needed, where the following would be collected in addition to the above:

- Measure Vital Signs & Orthostatic Blood Pressure, and Weight.
- Collect blood samples for clinical safety labs

#### Month 18 Visit

- Measure Vital Signs & Orthostatic Blood Pressure, Weight
- Administer Neuro/Motor Assessments per the SOA (Table 1)
- Administer SCOPA- AUT
- Administer Cognitive and Psychiatric Assessments: Cognitive Change and Cognitive Characterization State-Trait Anxiety Inventory for Adults, QUIP, Geriatric Depression Scale
- Digital Assessment per the PPMI Digital Sub Study (as needed)
- Perform Global Function Assessments: including CGI-S, PGI-S, PDAQ-27, Novel

Participant Reported Outcomes

- Collect blood samples for clinical safety labs
- Administer C-SSRS Since Last Visit Short Form
- Concomitant medication review
- LEDD medication initiation log (as needed)
- Assess and document AEs
- Current medical conditions review
- Report of Pregnancy (as needed)
- Surgery for PD (as needed)

#### Month 21 Visit

At month 21, a tele (audio/visual) visit will be performed, the following assessments will occur:

- Administer Neuro/Motor Assessments per SOA (Table 1)
- Administer Cognitive and Psychiatric Assessments: Cognitive Change and Cognitive Characterization
- Digital Assessment per the PPMI Digital Sub Study (as needed)
- Administer C-SSRS Since Last Visit Short Form
- Concomitant medication review
- LEDD medication initiation log (as needed)
- Assess and document AEs
- Current medical conditions review
- Report of Pregnancy (as needed)
- Surgery for PD (as needed)

Please note, this visit can be converted to an in-person visit if needed, where the following would be collected in addition to the above:

- Measure Vital Signs & Orthostatic Blood Pressure, and Weight.
- Collect blood samples for clinical safety labs

#### Month 24 Visit

- Perform physical examination
- Measure Vital Signs & Orthostatic Blood Pressure, Weight
- Administer Neuro/and Motor Assessments per the SOA (Table 1)
- Administer Non-Motor Assessments: Olfactory testing UPSIT, RBD Screening Questionnaire, Epworth Sleepiness Scale, SCOPA– AUT, Neuro QoL
- Administer Cognitive & Psychiatric Assessments per the SOA (Table 1)
- Digital Assessment per the PPMI Digital Sub Study (as needed)
- Perform Global Function Assessments: including CGI-S, PGI-S, PDAQ-27, Novel Participant Reported Outcomes

- Collect blood samples for clinical safety labs
- Perform 12-lead electrocardiogram
- Administer C-SSRS Since Last Visit Short Form
- Collect research samples (blood and urine)
- LP
- Skin Biopsy
- Dopamine Transporter Injection & SPECT Imaging (pregnancy test prior to DaTscan)
- MRI
- Concomitant medication review
- LEDD medication initiation log (as needed)
- Assess and document AEs
- Current medical conditions review
- Report of Pregnancy (as needed)
- Study Completion Form (if that is End of RSSP visit)
- Surgery for PD (as needed)
- Visit status

### 9.6 Additional Treatment Visits

All participants will continue on an every 3 months visit schedule in the randomized RSSP until the last recruited participant completes the 24-month assessment or until 24 months since randomization have passed (if terminated early).

Following Month 24, participants will continue study visits every 3 months until the last participant randomized in the RSSP has had the opportunity to complete 24 months of follow-up on intervention. Participants will repeat the Months 15 - 24 visit schedules until the End of RSSP Treatment (Table 4). Therefore, Month 27 will follow the same schedule of activities as Month 15; Month 30 will follow the same schedule of activities as Month 18; Month 33 will follow the same schedule of activities as Month 21; Month 36 will follow the same schedule of activities as Month 24 and so on.

Visit	Follow This Visit
(After Month 24, Prior to	Schedule of
End of RSSP Treatment)	Activities
Month 27	Month 15
Month 30	Month 18
Month 33	Month 21
Month 36	Month 24
Month 39	Month 15

 Table 4: Every 3-Month Visits After Month 24

Month 42	Month 18
Month 45	Month 21
Month 48	Month 24

## 9.7 Additional Safety Visits

Participants may have additional unscheduled visits if required for safety assessments. Additional details, including the timing of this visit can be found in the RSSP. At a minimum, these visits will involve an assessment and documentation of AEs and a review and documentation of concomitant medications.

## 9.8 Initiation of Dopaminergic Therapy Visit

In case the participants require initiation of dopaminergic therapy defined as Levodopa, dopamine agonists), an in-person visit should be scheduled prior to starting therapy. See schedule of activities in the SOA. If this visit occurs  $\leq$  90 days from the next in-clinic visit, replace this visit with the next in-clinic visit and follow the schedule of activities accordingly. The participants should be encouraged not to initiate dopaminergic therapy in between the in clinic P2P visits.

## 9.9 End of RSSP Treatment Visit

The schedule of activities for the End of RSSP Treatment Visit will follow the schedule listed in Section 9.5.

## 9.10 End of RSSP Treatment Safety Call

An End of RSSP Treatment Safety Call will be completed 30 days after end of treatment unless specified otherwise in the RSSP.

A safety follow-up call is required when a skin biopsy, LP, or DAT SPECT is performed. This follow-up phone call will assess adverse events occurring the day of and 2-3 days after the DAT SPECT, LP, or skin biopsy.

### 9.11 End of RSSP and Master Protocol

Participants will complete the RSSP after the last randomized participant has had the opportunity to complete 24 months on intervention or until 24 months since randomization have passed (if terminated early), and after all RSSP related activities have been completed. Participants who complete all activities for end of a specific RSSP may remain in the MP if they continue to meet all eligibility requirements described in Section 7 and wish to be screened for another RSSP as outlined in Section 8.4. Participants who complete their assigned RSSP and do not wish to be screened/ or do not qualify for another RSSP, will complete their enrollment in the Master Protocol and continue follow-up through the PPMI study. In those cases, end of RSSP visit will serve as the end of Master Protocol visit. The RSSP will be closed once all participants have completed the follow-up period.

## 9.12 Early Termination Visit (ET)

Participants who withdraw consent or early terminate from an RSSP will be asked to be seen for an in-person RSSP Early Termination Visit and complete Month 24 assessments.

The outcome measures that are required to be collected for each RSSP, and the timing of and activities for the RSSP Early Termination Visit and End of RSSP Treatment Safety Call, will be detailed in each respective RSSP.

All participants will continue to be enrolled in the PPMI observational study as per PPMI SOA regardless of enrollment status in the Master Protocol.

## **10. INVESTIGATIONAL PRODUCT**

Investigational products will be provided and tested in RSSPs from different regimen partners. Each intervention may have multiple arms, such as different dosages, frequencies, or routes of administration.

The RSSP will describe the nature of the intervention and its MoA including the mode and frequency of administration, dosage, the specific target population (to be selected within the predefined subsets of the Master Protocol), additional enrollment criteria (if any), and other specific intervention-related information and assessments (safety or other assessments) that may be in addition to those outlined in the Master Protocol. At a minimum, each RSSP will include:

- A description of RSSP specific trial treatment(s), the dosage and dosage regimen of the investigational product(s) and any known safety concerns.
- A description of the dosage form, packaging, and labeling of the investigational product(s)
- A description of RSSP specific "stopping rules" or "discontinuation criteria" for individual participants, parts of RSSP, and entire RSSP
- Accountability procedures for RSSP specific investigational product(s), including the placebo(s) and comparator(s), if any
- Maintenance of RSSP specific procedures for breaking codes
- The identification of RSSP specific data to be recorded on the associated RSSP CRFs.

Each active agent will have a matching placebo. All regimens will be compliant with the Master Protocol, which outlines the majority of all clinical, biomarker, and safety assessments, making a shared placebo group both desirable and feasible.

Packaging and labeling will follow Good Manufacturing Practices (GMP) regulations and distributed via a central pharmacy to each site.

## **10.1 Investigational Product Manufacturer**

Details identifying the investigational product manufacturer will be included in the corresponding RSSP.

## **10.2** Labeling and Packaging

Investigational product for each regimen will be provided by the regimen partner and will be described in the corresponding RSSP. Packaging and labeling will follow GMP regulations.

Samples of labels will be kept with the Trial Master Files.

The participants will be instructed to return all remaining investigational product including empty package material, if applicable, to the study site. Drug accountability will be performed as described in the pharmacy manual.

Details for packaging, labeling, and re-supply will be described in the corresponding RSSP.

## **10.3 Acquisition and Storage**

Investigational product for all interventions will be received at the study site by designated study staff, handled and stored safely and properly at the site pharmacy or other designated location, and kept in a secure location to which only the trial pharmacist and designated pharmacy staff, SI, and clinical staff have access. Upon receipt, the investigational product will be stored according to the instructions specified on the labels. Storage conditions will be adequately monitored and temperature in the area in which the investigational product is stored will be controlled, monitored, and recorded, at a minimum daily.

In accordance with local regulatory requirements, the SI, designated site staff, or head of the medical institution (where applicable) at each site must document the amount of investigational product dispensed and/or administered to RSSP participants, the amount received from the Central Pharmacy, and the amount destroyed upon completion of the RSSP. The SI is responsible for ensuring product accountability records are maintained throughout the course of the study. The research pharmacist or designated study staff will be responsible for maintaining an accurate record of the shipment and dispensing of investigational product in a drug accountability log.

Additional investigational product-specific details will be provided in the RSSP.

### **10.4 Destruction of Investigational Product**

Details on how the investigational product will be destroyed, who is responsible for the destruction, and how long documentation will be retained at sites, will be provided in the sub-protocol.

### **10.5 Concomitant Medications**

Details on medications that may not be taken during the trial will be included in the RSSP.

## **10.6 Treatment Compliance**

Compliance for each treatment will be defined in the specific sub-protocol. In cases of noncompliance, the participant will be reminded of the importance of taking the investigational product per protocol.

## **10.7 Dose Adjustment Criteria**

Dose adjustment criteria will be outlined in the RSSPs.

# **11. CLINICAL ASSESSMENTS**

Assessments will be performed at designated time-points throughout each RSSP for clinical evaluation. In addition to the assessments evaluated below, participants will provide information on their demographics, past medical history, as well as concomitant medication usage.

Description of the MDS-UPDRS Part III as one of the primary outcome measures is provided in Section 11.1. Refer to the PPMI Operations Manual for a detailed description of all clinical assessments and instructions for administration.

Details of any additional specific clinical assessments required for an intervention will be reported in the corresponding RSSP.

### 11.1 MDS-UPDRS

The primary endpoint will involve a comparison of the MDS-UPDRS over time. The MDS-UPDRS has four parts:

- Part I (Non-motor experiences of daily living), compromising:
  - Part IA concerning behaviors that are assessed by the Site Investigator with all pertinent information from patients and caregivers
  - Part IB that is completed by the patient with or without the aid of the caregiver, but independently of the SI
- Part II (Motor experiences of daily living), designed to be a self-administered questionnaire like Part 1B, but similarly can be reviewed by the SI to ensure completeness and clarity
- Part III (Motor examination) has instructions for the rater to give or demonstrate to the patient; it is completed by the clinician rater
- Part IV (Motor complications) to be completed by the clinician rater

Once participants initiate dopaminergic medications, participants will have an assessment of the motor exam (Part III) in both the practically defined dopaminergic medications OFF (6 hours post dose per PPMI protocol) and ON (based on the participant / SI defined best ON and/or approximately 1-hour post dose) states for designated visits per the schedule of activities. Only the OFF assessments will be used in the primary analyses. Participants will self-administer Parts IB and II, but will review responses for accuracy and clarity with the SI or coordinator. Parts IA, III, and IV must be conducted by the SI. All parts of the MDS-UPDRS will be conducted at study visits, as indicated on the schedule of activities. Ideally, the same SI should assess all participants in parts IA and III of the MDS-UPDRS at all study visits.

# **12. BIOLOGIC RESEARCH SAMPLING**

Refer to the P2P Biologics Manual for the detailed description of the biologic samples collected and processing instructions.

## **12.1 Blood Samples**

Whole blood (about 10 ml), serum (about 30 ml) and plasma (about 10 ml) will be collected as per Schedule of Activities to conduct proteomic, metabolomic, genetic and other research analyses. No more than 60 ml will be drawn at any visit, including both clinical safety labs and research blood samples.

It is strongly advised that the research blood samples are collected in a fasted state (i.e., minimum of 8 hours since last meal/food intake) to ensure the quality of samples for future analyses. If fasting is not possible, then participants should be advised to eat a low lipid diet. All research samples will be sent to a central biorepository to be stored indefinitely for research purposes. Samples will be made available to researchers to conduct analyses related to PD and other disorders. Participants will not receive any individual results of research analysis or testing conducted on the biologic samples.

# 12.2 Urine

Urine (about 10 ml) will be collected to conduct analyte analyses.

# **12.3** Lumbar Puncture / Cerebral Spinal Fluid (CSF)

The LP is performed by the SI, or another qualified clinician appointed by the SI. An LP for the collection of 15-20 ml of CSF will be conducted for all PPMI participants per the PPMI visit schedule unless there is evidence of clinically significant coagulopathy or thrombocytopenia that would interfere with the safe conduct of the procedure. See PPMI procedure manual for details. Additional LPs may be conducted if required for the specific RSSP.

If an LP procedure is performed, participants will also be contacted by phone 2 to 3 [business/working] days following an LP to assess for any adverse events. The CSF samples will be sent to a central biorepository to be stored indefinitely for research purposes. The CSF samples will be made available to researchers to conduct analyses related to PD and other disorders.

# 12.4 Skin Biopsy

The skin biopsy is performed by the SI, or another qualified clinician appointed by the SI. Skin biopsy will be performed as part of the PPMI SOA (Table 1) unless specified otherwise in the RSSP. See PPMI procedure manual for details. Additional skin biopsies may be conducted if required for the specific RSSP.

If skin punch biopsy is performed, it will be done under local anesthesia (lidocaine) in the posterior neck according to the Schedule of Activities. Up to two punches will be completed and the skin samples will be processed as described in the PPMI Biologics Manual and shipped to the central biorepository for storage and analysis. Remaining samples may be used to evaluate other proteins, analytes, or potential biomarkers. Participants will not receive any individual results of analysis or testing conducted on the skin samples. Participants will be monitored the day of the procedure for adverse events. Participants will also be contacted by phone 2 to 3 business days following a skin biopsy to assess for any adverse events.

# **13. IMAGING**

## **13.1 Dopamine Transporter (DAT) SPECT Imaging**

Refer to the PPMI SPECT Technical Operations manual (TOM) for a detailed description of the SPECT imaging procedures.

Participants will undergo dopamine transporter imaging to measure dopamine transporter binding using single photon emission computed tomography (SPECT). All new participants will undergo DAT SPECT imaging at Master Protocol screening visit and at annual visits. P2P can utilize a previously acquired scan completed as part of the PPMI study provided that it was performed within the allowed time window. Please, refer to the TOM for further details.

The DAT SPECT imaging procedure will be performed at the individual sites using DaTscan to target the dopamine transporter and all imaging data will be submitted for analysis to the Imaging core. DAT SPECT imaging eligibility will be determined using prespecified imaging cut-offs. DAT SPECT eligibility result will be made available to the participant's clinical site.

Women of childbearing potential must have a urine (or serum if required by the site) pregnancy test prior to injection of DaTscan. The result must be confirmed as negative prior to proceeding with the injection. Before the DaTscan injection, participants will be pre-treated with stable iodine (10 drops of a saturated solution of potassium iodide) to reduce the uptake of DaTscan by the thyroid. If the participant is allergic to iodine, then potassium perchlorate 400 mg) can be substituted for potassium iodide. Participants will be injected with up to 5 mCi of DaTscan. Within a 4-hour (+/- 30 minute) window following the injection, participants will undergo DAT SPECT imaging for approximately 30 minutes (or up to an hour if the participant moved during scanning).

Participants will be monitored by study personnel for adverse events on the day that a DAT SPECT is obtained. Participants will also be contacted by phone 2 to 3 [business/working] days following the injection/scan to assess adverse events.

DaTscan is being used "off-label" in the PPMI Clinical study. The imaging result obtained from the scan is not intended to provide information about a clinical diagnosis and will not be shared with participants.

## 13.2 Magnetic Resonance Imaging (MRI)

Participants will undergo an MRI brain scan at the RSSP screening visit and will also undergo follow up MRI scans as indicated in the visit schedule. P2P can utilize a previously acquired scan completed as part of the PPMI study provided that it was performed within a 6-month window.

At the discretion of the SI and Imaging staff, participants who have presence of pacemakers, aneurysm clips, artificial heart valves, ear implants, metal fragments or foreign objects in the eyes, skin or body or any other known contra-indication to MRI may be advised not to complete a RSSP screening visit (or follow-up) MRI scan, but these participants may still participate in the Master Protocol.

Refer to the PPMI MRI Technical Operations manual for a detailed description of the MRI imaging procedures.

## **13.3 Digital Assessment**

The PPMI Observational Study has associated sub-studies containing various digital assessments. If a participant is enrolled in one of the PPMI digital sub-studies, they will continue enrollment in that sub-study while enrolled in the Master Protocol. The data collected can be assessed in the Master Protocol to support associated exploratory endpoints. If a Master Protocol participant is not currently enrolled in a PPMI digital sub-study, the site coordinator will encourage the participants to enroll in such digital sub-studies, if available. In addition, other digital health technologies may be incorporated in the individual RSSPs (refer to RSSP for details).

## 14. ADVERSE EVENTS AND SERIOUS ADVERSE EVENTS

The AE definition and reporting procedures for this Master Protocol comply with all applicable US Food and Drug Administration (FDA) regulations and International Conference on Harmonization guidelines.

## 14.1 Adverse Events (AEs)

An AE is the development of an undesirable medical condition or the deterioration of a pre-existing medical condition. In clinical studies, an AE can include an undesirable medical condition occurring at any time, including baseline or washout periods, even if no RSSP treatment has been administered. A treatment-emergent adverse event (TEAE) is an AE that occurs following or during exposure to a pharmaceutical product, whether or not considered causally related to the product.

The SI will carefully monitor each participant throughout each RSSP for AEs. Participants will be monitored for AEs from the time they provide consent to the Master Protocol through the end of the RSSP or 30 days after end of treatment (whichever comes first). However, only AEs related to study procedures will be collected and reported during the period between consent and randomization to RSSP. AEs, whether or not, they are related to the RSSP of interest, must be recorded on forms provided by the sponsor.

Examples of AEs include: new conditions, worsening or pre-existing conditions, clinically significant abnormal physical examination signs (e.g., skin rash, peripheral edema, etc.), or clinically significant abnormal test results (e.g., lab values or vital signs). Stable chronic conditions (e.g., diabetes, arthritis) that are present prior to the start of the specific RSSP and do not worsen during the RSSP are NOT considered AEs. Chronic conditions that occur more frequently (for intermittent conditions) or with greater severity would be considered worsened and therefore would be recorded as AEs.

AEs are generally detected in two ways:

Clinical  $\rightarrow$  symptoms reported by the participant or signs detected on examination

Ancillary Tests  $\rightarrow$  abnormalities of vital signs, laboratory tests, and other diagnostic procedures

## 14.2 Serious Adverse Event (SAE)

An SAE is an AE that is fatal or life-threatening, or results in hospitalization, prolongation of hospitalization, persistent or significant disability/incapacity, or a congenital anomaly/birth defect. A life-threatening AE is an AE that, in the view of the SI, places the participant at immediate risk of death from the reaction, as it occurred. Important medical events that may not result in death, be life-threatening, or require hospitalization may be considered an SAE when, based upon appropriate medical judgment, they may jeopardize the participant and may require medical or surgical intervention to prevent one of the outcomes listed in this definition.

Inpatient admission in the absence of a precipitating, treatment-emergent, clinical adverse event is not subject to immediate reporting. For example:

- Admission for treatment of a pre-existing condition not associated with the development of a new adverse event.
- Social admission (e.g., participant has no place to sleep).
- Protocol-specific admission during a clinical study (e.g., for a procedure required by another study protocol).
- Optional admission not associated with a precipitating clinical adverse event (e.g., for elective cosmetic surgery).

Inpatient admission does not include the following:

- Emergency Room/Accident and Emergency/Casualty Department visits
- Outpatient/same-day/ambulatory procedures
- Observation/short-stay units
- Rehabilitation facilities
- Hospice facilities
- Respite care (e.g., caregiver relief)
- Skilled nursing facilities
- Nursing homes
- Custodial care facilities

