## 14.3 Assessing Relationship to RSSP Drug & Study Procedures

An SI with appropriate expertise must make the determination of relationship to the investigational product for each AE. The SI should decide whether, in his or her medical judgment, there is a reasonable possibility that the event may have been caused by the investigational product or study procedures (including imaging, LP, or skin biopsy). The assessment of the relationship of an AE to the RSSP drug or study procedures is a clinical decision based on all available information at the time the event is being documented. The following definitions of the relationship between the AE (including SAEs) drug and/or the study procedure should be considered:

- Unrelated No possible relationship
  - $\circ\,$  Concomitant illness, accident, or event with no reasonable association with treatment

- The temporal relationship between study procedure and the adverse event onset/course is unreasonable or incompatible, or a causal relationship to study procedure is implausible.
- Unlikely to be Related Not reasonably related, although a causal relationship cannot be ruled out.
  - The reaction has little or no temporal sequence from administration of treatment, and/or a more likely alternative etiology exists.
  - While the temporal relationship between study procedure and the adverse event onset/course does not preclude causality, there is a clear alternate cause that is more likely to have caused the adverse event than the study procedure.
- **Possibly Related** Causal relationship is uncertain.
  - The reaction follows a temporal sequence from administration of the treatment and follows a known response pattern to treatment; the reaction could have been produced by the treatment or could have been produced by the RSSP participant's clinical state, or by other modes of therapy administered to the participant [Suspected treatment-related AE]
  - The temporal relationship between study procedure and the adverse event onset/course is reasonable or unknown, and while other potential causes may not exist, a causal relationship to the study procedure does not appear probable.
- **Probably Related** High degree of certainty for causal relationship

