#### 14.5.2 Serious Adverse Event Reporting Requirements

All SAEs (related and unrelated) will be recorded in a similar manner to AEs, unless further defined in the RSSP. All SAEs must be reported by the SI within one business day of the first awareness of the event. The SI must complete, sign and date the SAE pages, verify the accuracy of the information recorded on the SAE pages with the corresponding source documents, and notify the safety department.

A Medical Monitor (MM) will work closely with the site to obtain additional follow-up information, if required or available. As additional information is obtained, one or more follow-up SAE forms should be completed. SAE notifications will be provided to the sponsor MJFF and IND, Inc.

Relevant regulatory authorities must be notified by the appropriate IND holders of certain events. It is the SI's responsibility to notify the IRB or Independent Ethics Committee (IEC) of all SAEs that occur at his or her site. SIs will also be notified of all unexpected, serious, drug-related events (7/15 Day Safety Reports) that occur during the clinical trial. Each site is responsible for notifying its IRB or IEC of these additional SAEs.

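### Section 14.2 ties immediate reporting of admissions to a treatment-emergent event, which conflicts with the one-business-day SAE rule for screening-procedure complications before the first dose

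*Protocol*

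**What the plan says.** Four statements in section 14 of the protocol bear on this.

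- Section 14.1 says an adverse event can occur "even if no RSSP treatment has been administered". It then limits what is gathered early: "only AEs related to study procedures will be collected and reported during the period between consent and randomization to RSSP". It also defines the qualifier: "A treatment-emergent adverse event (TEAE) is an AE that occurs following or during exposure to a pharmaceutical product".
- Section 14.2 opens with "An SAE is an AE that is fatal or life-threatening, or results in hospitalization", along with the usual other criteria and no condition that treatment has started.
- Section 14.2 continues: "Inpatient admission in the absence of a precipitating, treatment-emergent, clinical adverse event is not subject to immediate reporting". Four examples follow: treatment of a pre-existing condition with no new event, social admission, admission required by a study protocol, and optional admission such as elective surgery.
- Section 14.5.2 covers related and unrelated SAEs and says: "All SAEs must be reported by the SI within one business day of the first awareness of the event".

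Section 14.3 asks the site investigator to judge whether an event "may have been caused by the investigational product or study procedures (including imaging, LP, or skin biopsy"), so procedure complications are an anticipated class of event. Table 1 and section 9.1 place DAT SPECT at screening for both groups, and LP and skin biopsy at screening for Group B, subject to the repeat intervals in the Table 1 footnotes.

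**The concern.** Before randomization the only adverse events collected are those caused by study procedures, and these arise before any regimen drug has been given. The sentence in 14.2 makes immediate reporting of an admission depend on a treatment-emergent cause. On the usual meaning of that term, the exemption falls on the one class of event that the protocol collects in this period.

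What is at stake is timeliness. Under section 14.7 the independent medical monitor reviews an SAE within 24 hours of being notified, so a late site report means a late review. The escalation route in section 14.3 does not fill the gap, because it is triggered by a relationship to the investigational product and not to a procedure. Meanwhile the same screening procedures would be continuing in other participants at approximately 30 sites.

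**Working it through.** No figure in the plan is in question and no arithmetic applies. The check sets the rules side by side and runs one case through them.

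**Test case: a Group B participant is admitted with a complication of the screening LP, before the first dose.**

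1. Is it an adverse event? Yes. Section 14.1 includes events before any regimen treatment.
2. Is it collected? Yes. It is procedure-related and falls between consent and randomization (14.1).
3. Is it an SAE? Yes. It resulted in hospitalization (14.2, first sentence).
4. When is it due? Within one business day, related or not (14.5.2).
5. Does the 14.2 exemption apply? If the LP complication is not treatment-emergent, yes: the admission has no precipitating treatment-emergent event.

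Steps 4 and 5 give opposite instructions for the same event.

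**How far this extends depends on what *treatment-emergent* means.** Section 14.1 defines it by exposure to a pharmaceutical product, not to the regimen drug. Sections 12.4 and 13.1 show which procedures involve a drug.

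| Screening procedure | When done (Table 1 footnotes, 9.1) | Drug named in the protocol | Exempt if treatment means regimen drug | Exempt on 14.1's literal wording |
|---|---|---|---|---|
| LP | Group B; repeated if the last was 12 months or more before | none | yes | yes |
| Skin biopsy | Group B; repeated if the last was 12 months or more before | lidocaine | yes | arguably no |
| DAT SPECT | both groups; repeated if the last was 3 months or more before | DaTscan injection, iodide pre-treatment | yes | arguably no |

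Section 6.2 compares treatment-emergent events between active and placebo within each regimen, which points to the regimen drug. The literal wording of 14.1 points the other way. LP is the clearest case because the protocol names no drug for it.

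**Does the qualifier do any work?** All four examples under the 14.2 sentence are admissions with no new precipitating event. The fourth repeats the test and omits the qualifier. Deleting it would leave all four exempt and remove the conflict at step 5.

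**The case against.** The strongest reply is that 14.5.2 sets the reporting duty and has no exception, while 14.2 is a definitions section whose examples show that only admissions without a precipitating event were meant. A site that follows 14.5.2 will report. This largely stands as to intent, and it is why the point is one of wording. It does not remove the conflict. The examples are introduced as illustrations and do not limit the rule, and a site could reasonably treat the more specific sentence in 14.2 as governing admissions.

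Other safeguards also count. The exempting sentence concerns inpatient admission only. Section 14.2 does not treat emergency-room visits, same-day procedures or observation stays as inpatient admission. Fatal, life-threatening and disabling events are SAEs on other grounds. The medical monitor also reviews severe events in near real time (14.7). A telephone assessment 2-3 days after each LP, biopsy or scan, screening included, helps the site learn of complications. The regimen sub-protocols, which are not at hand, may define SAE reporting further.

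Three stronger readings are tempting and not supported:

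- A reader might infer that the protocol deliberately exempts serious procedure complications. The examples and the unconditional rule in 14.5.2 speak against that.
- A reader might extend the gap to the Month 12 and Month 24 procedures. Those follow dosing, so their complications would be treatment-emergent.
- A reader might apply an assumed admission rate to 250 participants per regimen (125 active plus at least 125 control). The documents give no such rate. LP and biopsy at screening are confined to Group B and repeated only after an interval, and the control participants are shared across regimens. That product would not measure anything in this plan.

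**Conclusion.** The conflict holds as one of wording. An admission for a screening-procedure complication before the first dose is reportable within one business day under 14.2 and 14.5.2, and exempt from immediate reporting under another sentence of 14.2. It is clearest for a Group B screening LP. It reaches the biopsy and the scan only if *treatment* means the regimen drug.

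The consequence is a possible delay in a safety report, partly mitigated by 14.5.2 and by the review of severe events in 14.7. Its frequency cannot be estimated from the documents, and it does not affect the efficacy conclusions. It should be corrected because it concerns serious complications of the protocol's own procedures and the correction is very small.

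**What to change.** Reconcile sections 14.1, 14.2 and 14.5.2 at the next amendment:

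- In the 14.2 sentence, delete *treatment-emergent*, so that only admissions with no precipitating clinical adverse event are exempt. All four listed examples remain exempt.
- Add that an admission precipitated by any adverse event collected under 14.1, including procedure-related events between Master Protocol consent and first dose, follows the one-business-day rule in 14.5.2.

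The second statement should be tied to events collected under 14.1 and not to every event from consent onward. Section 14.1 collects only procedure-related events before randomization, and a wider wording would create a new inconsistency.

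The cost is one deleted term, one cross-reference and at most a few additional prompt SAE reports.
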